The primary outcome measure of this study is the change in NIH PROMIS Pain Intensity Scale 3a scaled score one year after operation. The mean scaled score change at one year will be compared for each group (heavy weight mesh versus medium weight mesh). Patient reported outcomes within the AHSQC were evaluated for patients undergoing ventral hernia repair from July 2013 through August 2016. Twenty-three patients met criteria for medium weight mesh as defined in Table 1 and six patients meeting criteria for heavy weight mesh. Scaled score changes at one year after operation are summarized as below:

	Size	Mean	SD	Min	Lower Quartile	Median	Upper Quartile	Max
Medium weight (Group 1)	23	-10.3	10.9	30.7	41.9	46.3	53.3	71.8
Heavy weight (Group 2)	6	-7.5	6.3	30.7	41.7	47.8	53.2	54.5

Version #: 6

Date Submitted: May 29, 2018

NCT03082391

Using a two sample t-test allowing for unequal variance with equal sample sizes (1:1) group allocation of medium weight and heavyweight mesh, 160 patients per group will achieve a target power of 80% given an alpha of 0.05. Assuming a 10% loss to follow up at 1 year, a total of 352 patients will be recruited for this study (176 patients in each group).

STATISTICAL ANALYSIS

Categorical variables will be examined using Pearson's Chi-Square and all continuous variables will be examined using the non-parametric Wilcoxon signed rank test. The categorical variables will be reported using proportions and continuous variables will be reported using the median and the interquartile range.

Specific Aim 1: The Wilcoxon signed rank test will be performed to determine if the change from baseline to one-year follow-up is statistically significantly different between the medium weight and heavyweight mesh groups.

Specific Aim 2: The proportion of patients in each group reporting a hernia recurrence will be examined using Pearson's Chi-Square test to determine if there is a difference between the groups.

Specific Aim 3: The counts of the surgical site infections will be compared using Pearson's Chi-Square test to determine if an association exists between either type of mesh and frequency of SSI.

Specific Aim 4: The change in the HerQLes will be examined using the Wilcoxon signed rank test to determine if there is a difference in the quality of life after hernia repair for patients receiving medium weight vs heavyweight mesh.

Version #: 6

Date Submitted: May 29, 2018

NCT03082391

DATA SAFETY MONITORING BOARD

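### Recruiting 352 and losing the assumed 10% leaves about 158 patients per group, slightly below the plan's own 160 (minor arithmetic inconsistency)

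*Combined protocol and SAP*

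**What the plan says.** The point rests on two consecutive sentences under the heading Power Calculation in the combined protocol and SAP.

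- The endpoint being powered: "The primary outcome measure of this study is the change in NIH PROMIS Pain Intensity Scale 3a scaled score one year after operation".
- The planning data, given in that section's table as group size, mean change and SD: "Medium weight (Group 1) 23 -10.3 10.9" and "Heavy weight (Group 2) 6 -7.5 6.3".
- The method: "Using a two sample t-test allowing for unequal variance with equal sample sizes (1:1) group allocation".
- The requirement: "160 patients per group will achieve a target power of 80% given an alpha of 0.05".
- The allowance for loss: "Assuming a 10% loss to follow up at 1 year, a total of 352 patients will be recruited for this study", with "176 patients in each group".

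The plan prints no formula for getting from 160 to 176. No other section gives a different total, a further allowance, a replacement rule or an imputation rule that would make up a shortfall.

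**The concern.** A loss to follow-up of 10% is a fraction of the patients recruited. The recruitment target should therefore be large enough that 90% of it is at least the evaluable number required. Here 90% of the target falls just short. The three stated figures (160 evaluable per group, 10% loss, 352 recruited) cannot all hold.

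This is the sample-size statement for the primary outcome, and readers will take the three figures as a consistent set. What is at stake is the accuracy of that statement. The design, the analysis and the trial's ability to answer its question are not affected to any useful degree.

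**Working it through.** **Inputs**, all from the Power Calculation section: mean changes -10.3 and -7.5, so a difference of 2.8 points; SDs 10.9 and 6.3; 1:1 allocation; unequal-variance t-test; alpha 0.05; 160 per group; 10% loss; 176 per group and 352 in total. The plan does not state whether the test is one- or two-sided. Two-sided is assumed because it reproduces the plan's number: by the normal approximation, a one-sided test would need only 125 per group.

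**Step 1: reproduce the 160.** For n per group, the standard error of the difference is sqrt(10.9²/n + 6.3²/n) = sqrt(158.5/n). At n = 160 this is 0.9953, and the noncentrality is 2.8 / 0.9953 = 2.813. With Satterthwaite degrees of freedom and the noncentral t distribution:

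| Evaluable per group | Power |
|---|---|
| 160 | 80.03% |
| 159 | 79.78% |
| 158.4 | 79.63% |
| 158 | 79.53% |

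So 160 is the smallest number that reaches 80% by this method, and the plan's figure is reproduced exactly. (The normal approximation gives 159.)

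**Step 2: reproduce the 352.**
- Adding 10% to the evaluable number: 160 x 1.10 = 176 per group, 352 in total. This matches the plan.
- Dividing by the retained fraction: 160 / 0.90 = 177.8, rounded up to 178 per group, 356 in total. This does not match.

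**Step 3: apply the stated loss to the stated total.**
- 176 x 0.90 = 158.4 per group; 352 x 0.90 = 316.8 in total.
- Shortfall in evaluable patients: 160 - 158.4 = 1.6 per group, 3.2 in total.
- Loss that 352 can absorb: 1 - 320/352 = 9.1%.

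**Step 4: size of the effect.**
- Power: 80.03% - 79.63% = 0.40 percentage points. With 158 whole patients per group, 80.03% - 79.53% = 0.50 points.
- Recruitment: 356 - 352 = 4 patients, and 4/352 = 1.1%.
- Check on 356: 178 x 0.90 = 160.2 per group, which meets the requirement.

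**The case against.** The strongest objection is that the gap does not matter. Four points support it.

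1. **Precision.** The plan gives its target power as a whole number, and 79.6% rounds to it. A reader might infer that the stated 80% is not delivered. The documents do not support that, because they claim no decimal place.

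2. **Rounding of the inputs.** Means and SDs are printed to one decimal. A true difference of 2.75 or 2.85 would give 78.6% or 81.4% at 160 per group. With both SDs 0.05 lower, 158.4 per group would give 80.06%. The printed inputs therefore cannot show that 158.4 misses 80%. They show only that it is below the stated 160.

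3. **Uncertainty in the planning data.** The heavyweight SD comes from six patients. Assuming normality, its 95% interval is about 3.9 to 15.5, which moves power at 160 per group from about 86% to about 46%. The standard error of the pilot difference is sqrt(10.9²/23 + 6.3²/6) = 3.4, against an estimate of 2.8. Four more patients would not make the 80% more dependable.

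4. **The test.** These powers are for a t-test, whereas the Statistical Analysis section names a Wilcoxon test for Specific Aim 1. A corrected power to three digits would be over-precise for the planned analysis.

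All four stand, and they limit the point to a minor one. They do not remove it, because 176 less 10% is below 160 whatever the test, the SDs or the rounding of power. The telephone contact offered for the one-year follow-up may reduce loss, but the plan still assumes 10%.

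A reader might also take it as established that the sponsor multiplied where it should have divided. The exact match to 1.10 makes this likely, but no formula is printed, so it remains an inference. The inconsistency does not depend on how 176 was reached.

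**Conclusion.** The point holds as a minor arithmetic inconsistency. Under the plan's own 10% loss, 352 recruited leaves about 158 evaluable per group against a stated requirement of 160. The cost is about 0.4 of a percentage point of power, and no more than half a point if 158.4 is rounded down to 158.

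The mismatch itself rests only on the plan's 160, 10% and 352. The power figures rest in addition on the pilot difference and SDs, a t-test and a two-sided alpha of 0.05.

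It would be wrong to read this as a finding that the trial is materially underpowered. The actual one-year loss could easily differ from a round 10% by more than the 0.9 points that separate 9.1% from 10%.

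**What to change.** Correct the one sentence so that its figures agree. Any of these will do:

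- Keep 352 and state that it preserves 160 evaluable patients per group for loss of up to about 9%.
- Keep 352 and the 10% assumption, and state that about 158 per group are then expected to be evaluable.
- Keep both the 10% assumption and the 160, and state 178 per group, 356 in total.

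The first two cost one sentence and no patients; the third costs four more patients. The first is the simplest, since it depends only on 160 and 352 and needs no restated power. There is no need to insert a revised power such as 79.5% or 79.6%. It would also help to print the inflation formula used.

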Specific Aim #1: To determine if the use of a medium weight material leads to a decrease in pain intensity at one year following surgery. This will be assessed with the use of the NIH PROMIS 3a Pain Scale. The change in scaled score one year after operation will be calculated by comparison to the scaled score obtained at baseline for each patient. The mean change at one year will be compared for each group (heavyweight mesh and medium weight mesh).

Specific Aim #2: To determine if there is a difference in ventral hernia recurrence at one year following surgery. Hernia recurrence will be determined using the Ventral Hernia Recurrence Inventory, a validated questionnaire using patient-reported outcomes to determine hernia recurrence after repair.⁸

Specific Aim #3: To determine if there is a difference in the rate of deep surgical site infection at 30-days following surgery between the two mesh types. Definitions of wound events are per the Centers for Disease Control and were agreed upon by all participating surgeons. These wound outcomes will be recorded in the AHSQC database at 30 days as follows:

Deep Incisional SSI

A **deep incisional SSI** must meet the following criteria:

Infection occurs within 30 days after the operative procedure AND the infection involves deep soft tissues (e.g., fascial and muscle layers) of the incision AND patient has at least ONE of the following:

- a. purulent drainage from the deep incision but not from the organ/space component of the surgical site

Version #: 6

Date Submitted: May 29, 2018

NCT03082391

- b. a deep incision spontaneously dehisces or is deliberately opened by a surgeon AND is culture-positive or not cultured AND the patient has at least one of the following signs or symptoms: fever ($>38^{\circ}\text{C}$), or localized pain, or tenderness. A culture-negative finding does not meet this criterion.
- c. an abscess or other evidence of infection involving the deep incision is found on direct examination, during invasive procedure, or by histopathologic examination or imaging test.
- d. diagnosis of a deep incisional SSI by a surgeon or attending physician.

NOTE:

- a. Classify an infection that involves both superficial and deep incision sites as a deep incisional SSI.
- b. Classify infection that involves superficial incisional, deep incisional, and organ/space sites as deep incisional SSI. This is considered a complication of the incision.

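### The primary outcome is defined and sized on mean pain change, but the analysis section gives a rank test with medians and IQRs, and no between-arm estimate or confidence interval is specified

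*Combined protocol and SAP*

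**What the plan says.** The Power Calculation section defines the outcome: "The primary outcome measure of this study is the change in NIH PROMIS Pain Intensity Scale 3a scaled score one year after operation". It continues: "The mean scaled score change at one year will be compared for each group (heavy weight mesh versus medium weight mesh". Under Outcomes to Be Investigated, Specific Aim #1 says the same: "The mean change at one year will be compared for each group (heavyweight mesh and medium weight mesh".

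The sample size uses the same quantity. The registry rows, giving group size, mean and SD, are "Medium weight (Group 1) 23 -10.3 10.9" and "Heavy weight (Group 2) 6 -7.5 6.3". The method is "Using a two sample t-test allowing for unequal variance with equal sample sizes (1:1) group allocation of medium weight and heavyweight mesh", and the result is that "160 patients per group will achieve a target power of 80% given an alpha of 0.05".

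The Statistical Analysis section takes a different line. It assigns a Wilcoxon signed rank test to every continuous variable and states that "continuous variables will be reported using the median and the interquartile range". The Aim 1 paragraph repeats the Wilcoxon test and adds no mean, difference, other effect measure or interval. The primary outcome is not exempted from the reporting rule.

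**The concern.** Two sections commit to comparing means, and the trial is sized for that comparison. The section that governs analysis and reporting prescribes a rank test and medians, and does not say how the two fit together. An analyst who follows that section alone produces two medians, two IQRs and a p-value for the primary outcome.

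That output lacks the difference in mean change and any measure of its precision. A significant result could not be expressed on the scale used for planning. A non-significant result could not show how large a mean benefit of medium weight mesh remains compatible with the data. If the mean difference were added after the data had been seen, it would lack the standing of a pre-specified primary estimate. It would also be unclear whether the rank test or the comparison of means governs if they disagree.

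**Working it through.** **Inputs (Power Calculation table and text).** Medium weight: n = 23, mean change -10.3, SD 10.9. Heavyweight: n = 6, mean change -7.5, SD 6.3. Alpha 0.05, power 80%, 160 per group. Sidedness is not stated.

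**1. Reproduce the plan's figure.**
- Difference in means: -10.3 - (-7.5) = -2.8 points.
- SE at 160 per arm: sqrt((10.9² + 6.3²)/160) = sqrt(158.5/160) = 0.995.
- Noncentrality: 2.8/0.995 = 2.81.
- The Welch t-test (noncentral t, Satterthwaite degrees of freedom, two-sided 0.05) has power 80.03% at 160 per arm, and 160 is the smallest n that reaches 80%.
- A one-sided calculation (normal approximation) gives 125 per arm, which does not match.

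So 160 per group follows from a two-sided Welch comparison of means with a 2.8-point difference.

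**2. Precision available for the mean difference.**
- Planning SDs: half-width = 1.96 × 0.995 = 1.95 points.
- Common SD, pooling the 29 registry patients: sqrt((22 × 10.9² + 5 × 6.3²)/27) = 10.2; SE = 10.2 × sqrt(2/160) = 1.14; half-width = 2.24 points.

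**3. Can the arm medians stand in for the means?** Only under symmetry. If change scores are symmetric in each arm, the difference in medians equals the difference in means whatever the SDs. With skewness the two can part. The documents give no usable distribution of change scores: the minimum, quartile, median and maximum columns of the planning table run from 30.7 to 71.8 and cannot describe changes with means of -10.3 and -7.5.

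As an assumed illustration, take gamma-shaped changes (shape 2) with the plan's means and SDs:

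| Assumed shape | Median, medium | Median, heavy | Difference in medians | Difference in means |
|---|---|---|---|---|
| Left-skewed | -7.82 | -6.07 | -1.75 | -2.8 |
| Right-skewed | -12.78 | -8.93 | -3.85 | -2.8 |

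**4. Can the two tests disagree?** Simulation at 160 per arm (6,000 runs per case), taking the Wilcoxon test to mean a two-sample rank test:

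| Assumed shape | Power, rank test | Power, Welch |
|---|---|---|
| Normal | 78% | 80% |
| Left-skewed | 34% | 81% |
| Right-skewed | 99% | 79% |

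Under normality the choice hardly matters. Under skewness with unequal spreads the tests address different questions and can give different answers, so the plan has to say which one governs.

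**The case against.** The strongest reply is that the plan does commit to means. Aim 1 and the Power Calculation both say mean changes will be compared, and the median-and-IQR sentence is a general reporting rule that neither withdraws that commitment nor bars further summaries. This stands. A reader might infer that the trial will never report a mean difference, but the documents do not support that. They show a plan that contradicts itself and specifies no between-arm estimate or interval.

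Other stronger readings also fail:

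- *The unequal planning SDs by themselves make medians misleading.* They do not. Skewness is needed, and the documents neither show it nor rule it out. The gamma figures are illustration only.
- *The result should be judged against 2.8 points as a threshold.* The documents never call 2.8 a target or a clinically important difference. It is the gap between 23 and 6 registry patients, with SE sqrt(10.9²/23 + 6.3²/6) = 3.43 and a Welch 95% interval of about 2.8 ± 7.4, which includes zero. If the true difference were zero, the trial's interval would exclude a 2.8-point benefit about 80% of the time (Φ((2.8 - 1.95)/0.995)), or 69% with the common SD. The 80% is essentially the stated power seen from the other side and does not measure harm from the reporting rule.
- *Aim 4 has the same contradiction.* No section defines or powers HerQLes as a comparison of means.

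It is also fair to say that medians and IQRs are reasonable description for scores that may be skewed; the fix keeps them. Finally, adding a mean difference while a rank p-value still decided significance would replace one mismatch with another. That objection stands, and the fix therefore covers the test as well as the summary.

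**Conclusion.** The point holds as an inconsistency. The primary outcome is defined and sized as a difference in mean change. The analysis section supplies a rank test with medians and IQRs, makes no exception for the primary outcome, and no section specifies a between-arm effect estimate or a confidence interval.

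What is at stake is interpretation, not sample size. The data could give the mean difference to within about ±1.95 points, or ±2.24 with a common SD of 10.2; the analysis section as written does not ask for it. These half-widths assume 160 evaluable patients per arm and SDs from a small registry sample, one of them from six patients. How far medians would depart from means cannot be determined from the documents. The change should be made, because without it a null primary result would be hard to interpret.

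**What to change.** In the Statistical Analysis section, for Aim 1:

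- Report mean change (SD) per arm and the medium-minus-heavyweight difference in mean change with a two-sided 95% confidence interval allowing unequal variances. Name this the primary estimate.
- Make the matching unequal-variance comparison of means the primary test, in line with the sample-size calculation.
- Keep a two-sample rank test and the medians and IQRs as supportive, and state that the comparison of means governs.
- The 2.8-point planning difference may be cited as context for the interval, but not as a clinical threshold or decision rule.

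For Aim 4, a between-arm estimate with an interval is a useful optional addition; there is no contradiction there to repair.

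The cost is a few sentences. No new data, patients or procedures are needed, and 160 per group still gives 80.0% power for a 2.8-point mean difference on the planning SDs.

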The allocation of the patient to either a heavyweight or medium weight mesh will be performed in the operating room based on final CDC wound classification after the posterior components are reapproximated. Randomization will be performed according to a computer-generated block randomization scheme at each participating institution. The corresponding prosthetic material will then be placed with at least 5 cm of fascial coverage on all sides of the defect. The mesh will be fixed with mechanical sutures. Drains will be placed above the mesh, when utilized, and the timing of removal will be based on the surgeon's standard practice. Skin must be closed with either suture or staples. Fascial closure and management of the wound dressings will occur based on the surgeon's standard practice.

ANTICIPATED TIME FRAME

Version #: 6

Date Submitted: May 29, 2018

NCT03082391

Estimated patient accrual time is one year with data collection to occur over one year from the last enrolled patient. Data analysis and manuscript production will occur within six months of completion of data collection.

PATIENT RISKS AND DISCOMFORTS

As with any surgical procedure, there are some associated risks and they will be discussed in a separate surgical consent form. The subjects may experience some pain, bleeding and discomfort; however this is with any surgical operation. Common occurrences following hernia repair include seroma or hematoma around the hernia repair, inflammation, opening of the wound, or infection. Subjects may also experience additional therapies or treatments, including the removal of the mesh to treat any of these events.

PATIENT BENEFITS

There are no direct benefits to subjects for participating in this study. Subject participation will help us better understand the long-term outcomes of heavyweight and mediumweight mesh with respect to patient quality of life and hernia recurrence.

COSTS TO THE SUBJECTS

There are no extra costs to the subjects associated with the research. Procedures related to the preoperative evaluation and the hernia surgery are considered standard of care and will be the responsibility of the subject and the subject's insurance company.

Version #: 6

Date Submitted: May 29, 2018

NCT03082391

ALTERNATIVES TO PARTICIPATION

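### The primary pain comparison and the HerQLes comparison are assigned the Wilcoxon signed rank test, a paired test, although the two mesh arms are independent.

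*Combined protocol and SAP*

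**What the plan says.** The opening paragraph of the Statistical Analysis section sets a general rule: "all continuous variables will be examined using the non-parametric Wilcoxon signed rank test". Specific Aim 1, the primary outcome, repeats it: "The Wilcoxon signed rank test will be performed to determine if the change from baseline to one-year follow-up is statistically significantly different". That sentence goes on to make the question a contrast between the medium weight and heavyweight groups. Specific Aim 4 does the same: "The change in the HerQLes will be examined using the Wilcoxon signed rank test", in order to find a "difference in the quality of life after hernia repair for patients receiving medium weight vs heavyweight mesh".

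Three other parts of the document describe the same comparison:

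- Outcomes to be Investigated, Specific Aim #1, defines the endpoint patient by patient: "The change in scaled score one year after operation will be calculated by comparison to the scaled score obtained at baseline for each patient". It then compares the mean change between groups.
- Surgical Procedure describes the allocation: "Randomization will be performed according to a computer-generated block randomization scheme at each participating institution". No matching of patients across arms is described.
- Power Calculation sizes the comparison with a two-sample t-test with unequal variances, giving 160 patients per group.

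No section names a rank-sum (Mann-Whitney) test.

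**The concern.** The signed rank test takes one set of values, or one set of paired differences, and asks whether they are centred on zero. Subtracting baseline from the one-year score uses the only natural pairing in this trial. What remains is two independent samples of change scores, possibly of unequal size after loss to follow-up. The signed rank test has no defined way to contrast them.

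The test governs the primary hypothesis, that medium weight mesh gives less pain at one year. Both arms are expected to improve markedly, so within-arm tests would come out significant whether or not mesh weight matters. If the analyst instead substitutes another test, the choice is made outside the plan, possibly after the data have been seen.

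**Working it through.** **Inputs.** From the Power Calculation table: mean change -10.3 (SD 10.9, n=23) for medium weight and -7.5 (SD 6.3, n=6) for heavyweight. Also from that section: alpha 0.05, power 80%, 160 per group, 10% loss, 176 recruited per group. All simulations below assume normal change scores.

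**1. The plan's own figure.** The difference is 10.3 - 7.5 = 2.8. The root-mean-square SD is sqrt((10.9² + 6.3²)/2) = sqrt(79.25) = 8.90. The two-sided normal approximation is n = 2 × (1.960 + 0.842)² × 79.25 / 2.8² = 158.7, so 159. The Welch calculation with the noncentral t gives 160 (power 0.800). The stated 160 therefore reproduces, and it treats the arms as independent. Evaluable patients after 10% loss are 176 × 0.9 = 158.4, so 158 per arm.

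**2. Reading A: signed rank within each arm.** This tests change against zero. The mean change over its standard error is 10.3/(10.9/√158) = 11.9 for medium weight and 7.5/(6.3/√158) = 15.0 for heavyweight.
- At the plan's values with 158 per arm, p<0.001 occurred in both arms in 300 of 300 simulated trials.
- With no arm difference (common mean -8.9, the midpoint of -10.3 and -7.5, an assumption), the within-arm tests at 160 per arm rejected at 0.05 in 100% of 3,000 runs in each arm. So did the test on both arms pooled.
- The two within-arm p-values cannot be ranked against each other either. The standardized change is 10.3/10.9 = 0.94 for medium weight and 7.5/6.3 = 1.19 for heavyweight. The arm with the smaller mean improvement would tend to give the smaller p-value.

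**3. Reading B: signed rank on arbitrary cross-arm pairs.**
- At 160 per arm (3,000 runs), this rejected in 5.0% of runs with equal means and 78.4% at the planned difference. It does respond to the contrast.
- The answer depends on who is paired with whom. At the planned difference and 158 per arm (300 trials, 20 re-pairings each), the verdict at 0.05 changed with the pairing in about 24% of trials. Repeat runs gave about 21% and 22%. The simulation standard error is sqrt(0.24 × 0.76/300) = 2.5 points, so these agree. With equal means the figure was about 9%.
- In one simulated data set of 160 per arm, the central 95% of p-values over 2,000 pairings ran from 0.000015 to 0.00028.
- With unequal arms some patients must be left out, because the test needs complete pairs.

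**4. What a correct test costs.**

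| Test | Power at 160 per arm | Power at 158 per arm | Evaluable per arm for 80% |
|---|---|---|---|
| Welch t-test | 0.800 | 0.795 | 160 |
| Wilcoxon rank-sum | 0.778 | 0.774 | about 168 |

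The rank-sum powers are simulated (10,000 runs). The 168 is 160 × π/3 = 167.6, rounded up, from the asymptotic relative efficiency; simulated power at 168 was 0.796. With 10% loss, 168/0.9 = 186.7, so 187 per arm or 374 in total. With equal means and the planned unequal SDs, rank-sum rejected in 5.5% of runs.

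**The case against.** The strongest reply is that this is a misnomer. Aim 1 and Aim 4 both state a between-group question, the power section uses a two-sample test, and a competent analyst would read rank-sum. Using the term three times shows a consistent label, not an intention to run a paired analysis. Within-arm tests would contradict Aim 1's own sentence, so the 100% result describes a procedure the authors probably never meant. Random cross-arm pairing does address the contrast at close to the nominal error rate.

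Much of this is fair. The intended contrast is clear, and rank-sum is the likeliest intended test. Reading B fails because it is arbitrary and cannot use all patients in unequal arms, not because its error rate is wrong.

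It does not rescue the text. Rank-sum is not the only possible correction: the outcomes and power sections compare mean change and point to a t-test, whereas the analysis section is rank-based and reports medians. The plan therefore leaves open which test decides the primary hypothesis, and a silent substitution would be an undocumented departure from the prespecified analysis.

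**Conclusion.** The concern holds and must be fixed. The named test does not fit two independent arms, and it conflicts with the stated question, the randomization and the sample-size method. This follows from the design and needs no simulation. Read within arms, the test is uninformative about mesh weight. Read across arms, it gives a pairing-dependent verdict in roughly a fifth to a quarter of trials at the planned difference.

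Those sizes rest on normal change scores and on pilot means and SDs from 23 and 6 patients. The sample size of 160 per group is not in error for the two-sided Welch test. It falls short by about two percentage points of power if rank-sum is adopted.

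**What to change.** In the opening paragraph, Specific Aim 1 and Specific Aim 4 of the Statistical Analysis section, replace the signed rank test with one named test for two independent samples, and state that it is two-sided at 0.05. Choose it before outcome data are examined by arm. Either of two choices is sound:

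- **Wilcoxon rank-sum (Mann-Whitney) test on change from baseline.** This is the minimum edit and keeps the rank-based approach. Acknowledge power of about 77% to 78% at the planned size, or plan for about 187 recruited per arm.
- **Welch t-test on change from baseline.** This matches the mean-change endpoint and the existing power calculation. Report the mean difference with its confidence interval alongside the medians.

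A linear model adjusted for baseline score and site would also answer the question and reflects the blocking by institution, but it is optional here. Keep the signed rank test, if at all, only to describe change within an arm.

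The cost is a wording amendment. No new data are needed, and no extra patients unless the team chooses rank-sum and wants to restore 80% power.
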